13.1 Regulatory and ethical compliance

[figure not shown]
This clinical study was designed and shall be implemented, executed and reported in accordance with the ICH Harmonized Tripartite Guidelines for Good Clinical Practice, with applicable local regulations (including European Directive 2001/20/EC, US CFR 21), and with the ethical principles laid down in the Declaration of Helsinki.

13.2 Responsibilities of the investigator and IRB/IEC

Before initiating a trial, the investigator/institution must obtain approval/favorable opinion from the Institutional Review Board/Independent Ethics Committee (IRB/IEC) for the trial protocol, written informed consent form, consent form updates, participant recruitment procedures (e.g., advertisements) and any other written information to be provided to participants. Prior to study start, the investigator is required to sign a protocol signature page confirming his/her agreement to conduct the study in accordance with these documents and all of the instructions and procedures found in this protocol and to give access to all relevant data and records to Novartis monitors, auditors, Novartis Quality Assurance representatives, designated agents of Novartis, IRBs/IECs, and regulatory authorities as required. If an inspection of the clinical site is requested by a regulatory authority, the investigator must inform Novartis immediately that this request has been made.

13.3 Publication of study protocol and results

The protocol will be registered in a publicly accessible database such as clinicaltrials.gov and as required in EudraCT. In addition, after study completion and finalization of the study report

the results of this trial will be submitted for publication and posted in a publicly accessible database of clinical trial results, such as the Novartis clinical trial results website and all required Health Authority websites (e.g. Clinicaltrials.gov, EudraCT etc.)

For details on the Novartis publication policy including authorship criteria, please refer to the Novartis publication policy training materials that were provided to you at the trial investigator meetings.

13.4 Quality Control and Quality Assurance

Novartis maintains a robust Quality Management System (QMS) that includes all activities involved in quality assurance and quality control, to ensure compliance with written Standard Operating Procedures as well as applicable global/local GCP regulations and ICH Guidelines.

Audits of investigator sites, vendors, and Novartis systems are performed by auditors, independent from those involved in conducting, monitoring or performing quality control of the clinical trial. The clinical audit process uses a knowledge/risk based approach.

Audits are conducted to assess GCP compliance with global and local regulatory requirements, protocols and internal SOPs, and are performed according to written Novartis processes.

14 Protocol adherence

[figure not shown]
This protocol defines the study objectives, the study procedures and the data to be collected on study participants. Additional assessments required to ensure safety of participants should be administered as deemed necessary on a case by case basis. Under no circumstances including incidental collection is an investigator allowed to collect additional data or conduct any additional procedures for any purpose involving any investigational drugs under the protocol, other than the purpose of the study. If despite this interdiction prohibition, data, information, observation would be incidentally collected, the investigator shall immediately disclose it to Novartis and not use it for any purpose other than the study, except for the appropriate monitoring on study participants.

Investigators ascertain they will apply due diligence to avoid protocol deviations. If an investigator feels a protocol deviation would improve the conduct of the study this must be considered a protocol amendment, and unless such an amendment is agreed upon by Novartis and approved by the IRB/IEC and Health Authorities, where required, it cannot be implemented.

[figure not shown]

			Add one sensitivity analysis to investigate the impact of subjects with unexpected fluctuations	Section 2.5.4
			Delete the paragraphs for supportive analyses	Section 2.5.5
			Change the success criteria for gaining of 3 lines in binocular DNCVA	Section 2.7.2 Section 2.13 Section 4
			Add required part for CTSD	Section 2.8.1
			Remove the summary and shifting tables	Section 2.8.3 Section 2.8.4.2

Date	Time point	Reason for update	Outcome for update	Section and title impacted (Current)
			[REDACTED]	
			[REDACTED]	1
			Update the interim analysis team members	Section 2.14.2
			Add the description of Five Macros for multiple imputation	Section 5.4.1
			Remove the Type III analysis in logistic regression and add the sample code	Section 5.4.2
			[REDACTED]	
23- November- 2022	Prior to DB lock	Creation of amendment 2	Reflect early study termination	Section 1, Section 2.14, Section 4
			Delete second interim analysis	Section 1.1, Section 2.14
			Define end of study/end of treatment mapping rule	Section 2.1.1.3
			Define the wording of unscheduled visits mapping rule	Section 2.1.14
			Delete the summary of significant non-drug therapies and procedures	Section 2.4.1
			Define secondary endpoints	Section 2.7
			Defined safety endpoints	Section 2.8.1
			Delete “ i.e. until 1 day after the date of the last study treatment”	Section 2.8.1
			Add ophthalmic examinations and refractive status in the listings	Section 2.8.4.3
			[REDACTED]	[REDACTED]
			[REDACTED]	[REDACTED]

Date	Time point	Reason for update	Outcome for update	Section and title impacted (Current)
			Define changes to protocol analyses	Section 4
			Delete the imputation of CM end date for ongoing record	Section 5.1.2.1
			Delete medical history partial date of diagnosis imputation	Section 5.1.2.3

Table of contents

	Table of contents.....	6
	List of tables	8
	List of figures.....	8
	List of abbreviations	9
1	Introduction.....	11
1.1	Study design	11
1.2	Study objectives and endpoints	13
2	Statistical methods	15
2.1	Data analysis general information	15
2.1.1	General definitions	15
2.2	Analysis sets	18
2.2.1	Subgroups of interest	18
2.3	Patient disposition, demographics and other baseline characteristics	19
2.3.1	Subject disposition.....	19
2.3.2	Subject demographics and other baseline characteristics	19
2.4	Treatments (study treatment, concomitant therapies, compliance)	19
2.4.1	Prior, concomitant and post therapies.....	20

CTT	Clinical Trial Team
CRF	Case Report/Record Form (paper or electronic)
CSR	Clinical study report
DBL	Database Lock
DCNVA	Distance-corrected near visual acuity
DI-C&S	Novartis Development Informatics – Clinical and Safety Systems
ED50	Median Effective dose
EMA	European Medicines Agency
Emax	Maximum Effect
EOS	End of Study
ETDRS	Early Treatment Diabetic Retinopathy Study
FAS	Full Analysis Set
GPH	Global Program Head
IA	Interim Analysis
ICE	Intercurrent event
IRT	Interactive Response Technology
IAT	Interim Analysis Team
MAR	Missing at Random
MCP-Mod	Multiple Comparison Procedure - Modeling
MedDRA	Medical dictionary for regulatory activities
mg	milligram(s)
mL	milliliter(s)
MMRM	Multilevel Modelling for Repeated Measures
[REDACTED]	[REDACTED]
[REDACTED]	[REDACTED]
[REDACTED]	[REDACTED]
[REDACTED]	[REDACTED]
PD	Protocol Deviation
[REDACTED]	[REDACTED]
[REDACTED]	[REDACTED]
[REDACTED]	[REDACTED]
PT	Preferred term
SAE	Serious Adverse Event
SAF	Safety Set
SAP	Statistical Analysis Plan
SOC	System Organ Class

[REDACTED]
[REDACTED]

VA
WSE

[REDACTED]
[REDACTED]

Visual Acuity
Worse-seeing eye

1 Introduction

The study is being terminated early as Novartis has made the decision to stop UNR844A2202 for the treatment of presbyopia based on the results from the interim analysis. All subjects who are ongoing at the time of the decision of study termination will be discontinued from the study at their next visit.

The purpose of the Statistical Analysis Plan (SAP) is to describe the implementation of the statistical analysis planned in the study protocol, and to provide detailed statistical methods that will be used for the Clinical Study Report (CSR) of study CUNR844A2202.

The analyses will be conducted at two time points as described below:

- The Interim Analysis (IA) will be conducted on data from all subjects up to the Month 3 Visit, when all subjects complete (or discontinue prior to) the Month 3 Visit;
- The final analysis will be conducted on data obtained after Month 3 Visit once all active subjects have terminated the study and final Database Lock (DBL) achieved.

This document refers to the data analysis for:

- the Interim Analysis (at Month 3 visit), which is also the final analysis of the Month-3 endpoints;
- the final analysis for some key endpoints determined by the team, including data collected beyond Month-3.

Data will be analyzed according to the data analysis plan described in this document that will be incorporated into Section 9.7 and Appendix 16.1.9 of the CSR.

The Interim Analysis has been completed according to the plan on 24th August 2022.

1.1 Study design

This is a randomized, placebo-controlled, double-masked, multi-arm, parallel-group, multi-center study. The total duration of the study will be approximately 13 months and there will be around 225 male or female presbyopic participants aged 45 to 55 years enrolled in this study.

The 13-month study will consist of:

- A 1-week run-in period
- A 3-month treatment course with UNR844 and/or placebo
- A 9-month treatment holiday period

Participants will be randomized equally to one of five treatment arms, consisting of:

- Placebo eye drops, twice-a-day for three months
- UNR844 5 mg/mL eye drops, twice-a-day for three months
- UNR844 13.3 mg/mL eye drops, twice-a-day for three months

[figure not shown]
- UNR844 23 mg/mL eye drops, twice-a-day for three months
- UNR844 30 mg/mL eye drops, twice-a -day for three months

Participants will undergo a 1-week run-in period where they will be assessed for entry criteria during the Screening visit. During the run-in period, participants will administer 1 drop of artificial tears twice-a-day (1 drop in the morning and 1 drop in the evening) in each eye at home. This run-in period is designed to help minimize potential variability in distance-corrected near visual acuity (DCNVA) caused by initial ocular surface issues and help to establish an accurate baseline prior to randomization. The run-in period will exclude participants with a change in DCNVA more than 0.10 logMAR (5 letters) difference between Screening and Baseline. The study design is schematically depicted in [Figure 1-1](#).

Randomization will be stratified based on binocular DCNVA (0.50 logMAR or less; 0.52 logMAR or more) and age (45 to 50 years and 51 to 55 years) at baseline, and region. Participants will be randomized 1:1:1:1:1 within each stratum to one treatment arm. The randomization scheme for participants will be reviewed and approved by a member of the Randomization Office.

Figure 1-1 Study Design

CUNR844A2202 study

The primary objective of this study is to characterize dose-response of UNR844 in presbyopic subjects aged 45 to 55 years by assessing the change in binocular DCNVA from baseline after three months of treatment.

[figure not shown]
The interim analysis will be performed when all subjects completed (or discontinued prior to) the Month 3 visit to assess the primary objective. The analysis was completed and the outcome led to the discontinuation of the program due to lack of efficacy.

1.2 Study objectives and endpoints

Table 1-1 Objectives and related endpoints

Objective(s)	Endpoint(s)
Primary objective(s)	Endpoint(s) for primary objective(s)

Objective(s)	Endpoint(s)

• Characterize the dose-response of UNR844 for change from baseline in binocular DCNVA at Month 3	
• Change from baseline in binocular DCNVA assessed using letters at Month 3
Secondary objective(s)	Endpoint(s) for secondary objective(s)

• Characterize the dose response of UNR844 as measured by change from baseline in monocular DCNVA at Month 3• Assess the duration of effect using change in DCNVA after Month 3 with various dose concentrations of UNR844• Evaluate the efficacy of improving DCNVA in presbyopic participants, as measured by proportion of participants gaining at least 0.30 logMAR DCNVA at Month 3	
• Change from baseline in monocular DCNVA, assessed using letters (i.e. worse-seeing eye and better-seeing eye) at Month 3• Binocular and monocular DCNVA assessed using letters, over time after Month 3 (i.e. Month 4 to Month 12)• Proportion of participants gaining at least 0.30 logMAR in binocular and monocular (worse-seeing eye and better-seeing eye) DCNVA assessed using letters (without near correction) from baseline at Month 3

2 Statistical methods

2.1 Data analysis general information

The Interim Analysis will be performed by independent Analytics and statistical programming group of Novartis, while the final analysis will be performed by the Biostatistics and statistical programming of the CTT.

This document refers to the data analysis for the Interim Analysis (at Month 3 visit), which is also the final analysis of the Month-3 endpoints, as well as the final analysis, including data beyond Month-3. Analyses will be performed using SAS 9.4. In addition, the dose finding R package will be used for the dose finding analysis focusing on Month-3 endpoint.

Categorical data will be presented as frequencies and percentages. For continuous data, mean, standard deviation, median, minimum, and maximum will be presented. These summary statistics will be presented by treatment group unless otherwise specified. Where appropriate, point estimates and confidence intervals of treatment group differences will be provided.

In general, the randomization stratification factors will be included as factors in the primary efficacy analysis, and the corresponding supportive analyses.

2.1.1 General definitions

2.1.1.1 Study treatment

The following treatment groups will be presented:

- Placebo eye drops, one drop twice-a-day for three months
- UNR844 5 mg/mL eye drops, one drop twice-a-day for three months
- UNR844 13.3 mg/mL eye drops, one drop twice-a-day for three months
- UNR844 23 mg/mL eye drops, one drop twice-a-day for three months
- UNR844 30 mg/mL eye drops, one drop twice-a-day for three months

2.1.1.2 Baseline and post-Baseline

Baseline (Day 1) is the first study treatment in the study. The baseline value for efficacy and safety variables is the last available value (scheduled or unscheduled) collected prior to or at the date of first study treatment.

All data collected after the date of first study treatment are defined as post-baseline.

The *study day* for a baseline or post-baseline, scheduled or unscheduled visit, is defined as:

$Study\ day = (Date\ of\ visit) - (Date\ of\ first\ study\ treatment) + 1;$

The *study day* for a scheduled or unscheduled visit before baseline is defined as:

$Study\ day = (Date\ of\ visit) - (Date\ of\ first\ study\ treatment).$

2.1.1.3 End of study/end of treatment mapping

The *end of study* date (from 'Study disposition' CRF) is the date when a subject completes or discontinues the study. The *end of treatment* date (from 'Treatment disposition' CRF) is the date when a subject completes or discontinues the treatment.

To report data by visit in the outputs, the end of study with early discontinuation will be allocated to Month 12 /End of Study (Month 12/EOS) visit. To be more specific, any visit name equal to "Early Exit Visit" will be allocated to "Month 12/EOS" and analyzed as "Month 12/EOS".

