Women of child bearing potential must be informed that taking the study treatment may involve unknown risks to the fetus if pregnancy were to occur during the study and agree that in order to participate in the study they must adhere to the contraception requirements.

A copy of the approved version of all consent forms must be provided to Novartis after IRB/IEC approval.

Participants might be asked to complete an optional questionnaire to provide feedback on their clinical trial experience.

8 Visit schedule and assessments

The Assessment Schedule ([Table 8-1](#)) lists all of the assessments when they are performed. All data obtained from these assessments must be supported in the participant's source documentation.

Participants should be seen for all visits/assessments as outlined in the assessment schedule ([Table 8-1](#)) or as close to the designated day/time as possible. Missed or rescheduled visits should not lead to automatic discontinuation. Participants who prematurely discontinue the study for any reason should be scheduled for a visit as soon as possible, at which time all of the assessments listed for the final visit will be performed. At this final visit, all dispensed investigational product should be reconciled, and the adverse event and concomitant medications recorded on the CRF.

Assessments assigned to the screening visit can be conducted on separate days as close to each other as possible. Visual acuity and refraction assessments must be performed on the same day.

According to evaluation performed for this study all visits must be performed at site. No evaluation at home is possible with the exception of the [REDACTED], in case of COVID pandemic.

If the COVID-19 pandemic limits or prevents on-site study visits and other study assessments may not be performed, alternative methods of safety monitoring may be implemented. Depending on local regulations, site capabilities and participant's visit status in the study, phone calls or virtual contacts (e.g., teleconsult) can be performed for safety follow-up for the duration of the pandemic, until it is safe for the participant to visit the site again.

If a participant is unable to attend the scheduled baseline visit due to illness, the run-in period could be extended up to 2 weeks from the Screening visit. During this extended run-in period, participants will continue to administer the Sponsor provided artificial tears as directed.

[figure not shown]
[figure not shown]

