Table 8-1 Assessment Schedule

Period	Run-in	Treatment					Treatment holiday period									
Visit Name	Screening	Baseline	W2	M1	M2	M3	M4	M5	M6	M7	M8	M9	M10	M11	M12/EOS	
Days	-7	1	14	30	60	90	120	150	180	210	240	270	300	330	360	
Informed consent	X															
Demography	X															
Medical history/current medical conditions	X															
Prior medications	X	X														
Concomitant medications	X	X	X	X	X	X	X	X	X	X	X	X	X	X	X	
Inclusion/Exclusion criteria	X	X														
Vital Signs	X	X				X			X			X			X	
Physical Examination ¹	X														X	
Distance-corrected near visual acuity (letters) ³	X	X	X	X	X	X	X	X	X	X	X	X	X	X	X	

Period	Run-in	Treatment					Treatment holiday period									
Visit Name	Screening	Baseline	W2	M1	M2	M3	M4	M5	M6	M7	M8	M9	M10	M11	M12/EOS	
Days	-7	1	14	30	60	90	120	150	180	210	240	270	300	330	360	
IDEEL blurry vision question ¹	X															
Cycloplegic refraction	X															
Pupil size (non-dilated)	X															
Slit lamp biomicroscopy	X	X	X	X	X	X	X	X	X	X	X	X	X	X	X	
Corneal Staining	X	X	X			X						X			X	
Intraocular Pressure (IOP)	X	X	X	X	X	X	X		X			X			X	
Dilated fundus exam	X					X									X	
Hematology	X					X										
Clinical Chemistry	X					X										
Urinalysis	X					X										
Pregnancy Test (serum)	X															
Pregnancy Test (urine) ¹						X									X	
Adverse Events	X	X	X	X	X	X	X	X	X	X	X	X	X	X	X	
Drug dispensation		X		X	X											
Study completion information															X	
eDiary compliance assessment		X	X	X	X	X										

Period	Run-in	Treatment					Treatment holiday period								
Visit Name	Screening	Baseline	W2	M1	M2	M3	M4	M5	M6	M7	M8	M9	M10	M11	M12/EOS
Days	-7	1	14	30	60	90	120	150	180	210	240	270	300	330	360

^X Assessment to be recorded in the clinical database or received electronically from a vendor

[figure not shown]
¹ Assessment to be recorded in the source documentation only

█ [REDACTED]

³ Duplicate binocular DCNVA assessments will be completed at all visits

█ [REDACTED]

█ [REDACTED]

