12.5 Analysis of secondary endpoints/estimands

12.5.1 Efficacy and/or Pharmacodynamic endpoint(s)

There are three secondary endpoints:

1. Change from baseline in monocular DCNVA (i.e., worse-seeing eye and better-seeing eye) at Month 3;

- MCP-Mod as described in [Section 12.4.2](#) will be applied to change from baseline in monocular DCNVA at Month 3 for the worse-seeing eye (WSE) and better-seeing eye (BSE), with intercurrent events and missing data handled in the same way as the for the primary estimand and supportive estimand 2 ([Section 12.4](#))

2. Gain of 3 lines (change from baseline of ≤ -0.3 logMAR) in binocular, worse-seeing eye and better-seeing eye respectively at Month 3;
 - For monocular DCNVA, gaining of 3 lines is defined as change from baseline ≤ -0.3 logMAR in DCNVA and $< +0.1$ logMAR in BCDVA.
 - For the endpoints of gaining of 3 lines (change from baseline of 0.3 logMAR) in binocular, worse-seeing eye and better-seeing eye respectively at Month 3, missing data imputation will be done in the same way as for the primary endpoint (Section 12.4), defined for the primary estimand, based on their corresponding continuous endpoints, i.e., binocular and monocular DCNVA. After the imputation, these endpoints will be dichotomized to generate the endpoints of gaining of 3 lines in both eyes, worse-seeing eye and better-seeing eye, respectively at Month 3. Then a logistic regression model, by adjusting for baseline DCNVA and age (grouped as 45 to 50 years and 51 to 55 years), will be fitted to each imputed data set for each of the three endpoints. By applying Rubin's rule to combine results of these individual data sets, pairwise comparison of each dose versus placebo will be obtained for each of the three endpoints.
3. Change from Month 3 in binocular and monocular (worse-seeing and better-seeing eyes) DCNVA over time after Month 3 (i.e., Month 4 to Month 12).

For binocular, worse-seeing and better-seeing eyes, DCNVA over time after Month 3 will be summarized by treatment group and scheduled visits.

[figure not shown]
For DCNVA data (during treatment and treatment holiday), an individualized nonlinear mixed effect model will be used to describe the data and results will be provided in a separate modeling analysis report and not in the study CSR.

[figure not shown]
[figure not shown]

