2.1.1.4 Unscheduled visits

Data collected at unscheduled visits will only be used in ‘by-visit’ tabulations, graphs or analyses when it can be mapped to a missed scheduled visit by the 1/3 – 2/3 rule mentioned above. If multiple unscheduled visits are allocated to the same missed scheduled visit:

- The unscheduled visit closest to the missed scheduled visit will be used;
- If there are multiple unscheduled visits with the same distance/interval to the missed scheduled visit, the latest one will be used;

To be more specific, suppose such a visit falls between two adjacent scheduled visits (e.g. visits A and B) corresponding to visit days X and Y. If the assessment day of such a visit falls within rounding ($1/3*(Y-X+1)$) after Day X, then it will be allocated to visit A, otherwise, it will be allocated to visit B. Figure 2-1 shows a graphical illustration of how this 1/3 – 2/3 rule of visit allocation is done.

Table 2-1 shows an example of the allocation of end of study/end of treatment visit to a scheduled main visit, when an assessment is scheduled to be done at every scheduled visit; and Table 2-2 shows another example of visit allocation when an assessment is only done at Baseline, Month 1 - 4, 7, 10 and 12.

All data collected at unscheduled visits will be listed.

Figure 2-1 Graphical illustration of visit allocation using the 1/3 – 2/3 rule

[figure not shown]

Table 2-1 Allocation of unscheduled visit for an assessment to be done at each scheduled visit

Scheduled main visit name/label	Scheduled visit study day	Scheduled visit window in days	Comment
Screening	-7	-7 – -1	Screening
Baseline	1	1	Baseline
W2	14	2 – 19	
M1	30	20 – 40	
M2	60	41 – 70	

M3	90	71 – 100
M4	120	101 – 130
M5	150	131 – 160
M6	180	161 – 190
M7	210	191 – 220
M8	240	221 – 250
M9	270	251 – 280
M10	300	281 – 310
M11	330	311 – 340
M12	360	>=341

Table 2-2 Allocation of unscheduled visit for an assessment to be done at Baseline, Month 1-4, 7, 10, and 12

Scheduled main visit name/label	Scheduled visit study day	Scheduled visit window in days	Comment
Baseline	1	1	Baseline
M1	30	2 – 40	
M2	60	41 – 70	
M3	90	71 – 100	
M4	120	101 – 150	
M7	210	151 – 240	
M10	300	241 – 320	
M12	360	>= 321	

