2.7.1 Secondary endpoints

The corresponding secondary endpoints are:

1. Change from baseline in monocular DCNVA assessed using letters (i.e. worse-seeing eye and better-seeing eye) at Month 3;
2. Binocular and monocular (worse-seeing eye and better-seeing eye) DCNVA assessed using letters over time after Month 3 (i.e. Month 4 to Month 12);
3. Proportion of participants gaining at least 0.30 logMAR in binocular and monocular (worse-seeing eye and better-seeing eye) DCNVA assessed using letters (without near correction) from baseline at Month 3.

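### SAP 2.1.1.3 analyses every Early Exit Visit as Month 12/EOS whatever its study day, so an exit on Day 101–340 is placed 20 to 259 days late in by-visit summaries

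*SAP*

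**What the plan says.** SAP 2.1.1.3 sets the rule for by-visit outputs: "the end of study with early discontinuation will be allocated to Month 12 /End of Study (Month 12/EOS) visit". It then specifies that any visit carrying the name Early Exit Visit is analysed under the Month 12/EOS label. Study day plays no part.

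SAP 2.1.1.4 gives the window rule for unscheduled visits, but introduces its first table differently: "Table 2-1 shows an example of the allocation of end of study/end of treatment visit to a scheduled main visit". In Table 2-1, Months 4 to 11 occupy Day 101 to Day 340 in 30-day windows, and Month 12 starts at Day 341. In Table 2-2, for assessments done less often, Month 12 starts at Day 321.

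Four other places decide which data the rule reaches:

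- Protocol Table 8-1 schedules DCNVA at every visit, with the footnote "Duplicate binocular DCNVA assessments will be completed at all visits".
- Protocol Section 8 asks for a visit as soon as possible after premature discontinuation, "at which time all of the assessments listed for the final visit will be performed".
- SAP Section 1, on early termination: "All subjects who are ongoing at the time of the decision of study termination will be discontinued from the study at their next visit".
- SAP 2.7.1 keeps binocular and monocular DCNVA from Month 4 to Month 12 as a secondary endpoint. Protocol 12.5.1 plans that "DCNVA over time after Month 3 will be summarized by treatment group and scheduled visits", and separately that "an individualized nonlinear mixed effect model will be used to describe the data".

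**The concern.** The endpoint is about duration of effect after treatment stops, so time since treatment is the axis of interest. Under 2.1.1.3, a DCNVA value measured at Month 4 and one measured at Month 12 enter the same row. Three things follow:

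- The Month 12/EOS row mixes follow-up times.
- Its n overstates how many subjects were followed for 12 months.
- Where the exit visit stands in for a scheduled visit that was missed, the month actually attended loses its record.

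The reader cannot undo this from the planned outputs. The composite label does not separate the two kinds of record. The disposition summary in SAP 2.3.1 is described as giving counts and reasons, not exit timing.

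Ordinary drop-outs in the treatment holiday are covered by the rule if their last visit carries that name. Subjects leaving at their next visit after termination would be covered too, but only if those visits are recorded as Early Exit Visit, which the documents do not say.

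**Working it through.** **Inputs.** Nominal days, windows and the 1/3–2/3 formula come from SAP 2.1.1.4, Tables 2-1 and 2-2. The mapping of exits comes from SAP 2.1.1.3.

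**Step 1: reproduce the SAP's windows.** For adjacent visits on Day X and Day Y, the last day given to the earlier visit is X + round((Y − X + 1)/3).

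- M3 to M4: 90 + round(31/3) = 90 + 10 = 100, so M4 opens at Day 101.
- M11 to M12: 330 + round(31/3) = 330 + 10 = 340, so M12 opens at Day 341.
- Table 2-2, M10 to M12: 300 + round(61/3) = 300 + 20 = 320, so M12 opens at Day 321.

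All three agree with the printed tables.

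**Step 2: distance under the existing windows.** In each M4–M11 window the first day is 19 days before nominal (for M4, 120 − 101 = 19) and the last day is 10 days after it (130 − 120 = 10). The largest distance is therefore 19 days.

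**Step 3: distance under 2.1.1.3.** Days late = 360 − actual exit day.

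| Table 2-1 month | Window (study day) | Days late if shown at Day 360 |
|---|---|---|
| M4 | 101–130 | 230–259 |
| M5 | 131–160 | 200–229 |
| M6 | 161–190 | 170–199 |
| M7 | 191–220 | 140–169 |
| M8 | 221–250 | 110–139 |
| M9 | 251–280 | 80–109 |
| M10 | 281–310 | 50–79 |
| M11 | 311–340 | 20–49 |

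The range is 360 − 340 = 20 to 360 − 101 = 259 days. It is measured to the nominal day. Measured to the start of the M12 window, it is 341 − 340 = 1 to 341 − 101 = 240 days. For Table 2-2 assessments, exits on Day 101–320 are shown 360 − 320 = 40 to 259 days late.

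**Step 4: one day under both rules.** On Day 205, an unscheduled visit goes to M7 if M7 was missed, 210 − 205 = 5 days from nominal. An Early Exit Visit on the same day goes to Month 12/EOS, 360 − 205 = 155 days from nominal.

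**Step 5: effect on the row.** Suppose 10% of the Month 12/EOS row consists of Day 101–340 exits and the other records lie at Day 360. The row's mean study day then moves earlier by 0.10 × 20 = 2 to 0.10 × 259 = 25.9 days. The 10% is illustrative; the documents give no exit counts.

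**Step 6: is Month 3 touched?** SAP Section 1 records the interim analysis as completed on 24 August 2022. The SAP's amendment history dates amendment 2, which defined this mapping, to 23 November 2022. The rule also catches exits before Day 101, but the completed Month 3 analysis is not shown to have used it.

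**The case against.** The best defence is that 2.1.1.3 is the specific rule for exits and 2.1.1.4 governs only unscheduled visits. The heading of 2.1.1.4 and the titles of both tables say so, and amendment 2 lists the two rules as separate items. On that reading, the mention of end-of-study visits before Table 2-1 is a drafting leftover. This is plausible, and it would turn the contradiction into a wording error. It would not cure the consequence, because following 2.1.1.3 alone still puts Month 4 exits in the Month 12 row.

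A second point is that Month 12/EOS is openly a composite label, shared with Protocol Table 8-1, and that pooling exit and final visits is a sensible convention for final-visit items such as the physical examination or dilated fundus examination. That stands for those items. It does not suit a DCNVA time course.

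Third, the impact cannot be seen in full. In the copy available for this review, the text under SAP 2.7.2 item 3 is not visible after its heading. SAP Section 4 says analyses were simplified after termination. The planned nonlinear model may use actual visit dates, but this is not stated. A month also loses a record only if its scheduled visit was missed. These limits hold. They bound the consequence without removing the fault in the rule.

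**Conclusion.** The concern holds. As written, the SAP analyses every Early Exit Visit as Month 12/EOS, while the text introducing Table 2-1 points to windows that would place Day 101–340 exits in Months 4 to 11. The misplacement is 20 to 259 days against nominal Day 360, compared with at most 19 days under the existing windows.

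The number of subjects affected, and any bias in drug–placebo differences, cannot be determined: enrolment dates, exit counts and recorded visit names are not given. If the drug effect is absent or constant over time, and exit timing is similar across arms, the difference between drug and placebo is not biased, and the fault is confined to mislabelled timing and n. The endpoint carries no formal test. This should be fixed before the post-Month 3 by-visit outputs are produced, but it does not call the Month 3 result into question.

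**What to change.** In SAP 2.1.1.3, allocate Early Exit Visits for by-visit summaries by study day, using the Table 2-1 or Table 2-2 windows, when the corresponding scheduled visit was missed. Keep Month 12 for visits inside its window: Day 341 or later in Table 2-1, Day 321 or later in Table 2-2. Show exit records that cannot be placed, because the scheduled visit was already attended or the assessment was not due that month, in a separate end-of-study/last-visit row. Amend the sentence in 2.1.1.4 that applies Table 2-1 to end-of-study visits so that it agrees.

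The cost is one revised rule, a collision rule, one extra table row, a wording correction and a re-programmed visit mapping. Month 12 counts will be smaller. The windows already exist.
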